Physiotherapist consent and background data will be collected via Webropol questionnaires prior to the start of patient recruitment. English language copies of the data collection questionnaires (patient and physiotherapist PROMs and PREMs) are available from the corresponding author on request. The physiotherapists' evaluations of the initial consultation will be sent to the study coordinators via the messenger function of the electronic journal system within RÖ and RJL. All physiotherapists who have conducted at least one initial PainSMART consultation in the RCT will be sent a follow up Webropol questionnaire containing four questions. These four questions ask the physiotherapists to self-report their adherence to the study protocol for each group and rate their experiences of the participating patients' degree of preparedness for the initial consultations. For physiotherapists who consent to continue participation in the RCT for the qualitative phase, additional data will be collected via Dictaphone audio recordings of the initial physiotherapy consultation. The audio recordings will then be uploaded to Linköping University's secure NextCloud service.

Sample size

The sample size calculation for this study is based on its primary hypotheses. The calculations are based on the MCID of $2 \pm SD/4$ for the NRS for pain intensity and a minimal detectable change of $11.52 \pm SD/23.20$ for the PSEQ-10 (Dube et al., 2021; Olsen et al., 2017; Olsen et al., 2018; Ostelo et al., 2008). Sample size calculations were computed for both primary outcomes (NRS and PSEQ-10) using a Cohen's f effect size of = 0.25 (i.e. small-moderate) and a one-sided p-value of $p=0.05$ plus a statistical strength of 0.8 (=Power 80%). The largest sample size calculated was for analysis of the NRS ($n = 102$ per group) and this was adopted as the sample size for this study. To enable mediation and sub-group analyses two subgroups are required. This gives a total sample size of 408 patients. A drop-out rate of approximately 30% was factored into the randomisation sequence giving a total sample of 600 patients.

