
effect on pain self-efficacy is hypothesised to mediate the effects on health outcomes. A secondary objective is to explore if pain self-efficacy mediates the effect of the PainSMART-strategy on health outcomes of interest. The mediation models will be estimated using path-analyses within the framework of Structural Equation Modelling.

Analysis of patient and physiotherapist experience outcomes (PREMs)

The intervention group's scores related to the clarity of the film's key messages will be presented descriptively.

Outcomes relating to the evaluations of the initial physiotherapy consultation will be analysed through descriptive statistics and between group differences for each question. Additional analysis will be conducted for concordance between the patients and physiotherapists ratings on the three paired questions for each group.

Physiotherapists' experiences of their perception of the participating patients' preparedness for the initial consultation will be analysed through descriptive statistics and between group differences.

Analysis of physiotherapist adherence

Data on the physiotherapists' self-reported adherence to the protocol will be cross-referenced with the film, respective control, group consultations each individual physiotherapist has conducted. This, in combination with the film group patients' self-reported exposure to the film, will provide data indicating how many of the participating patients received the full PaintSMART-strategy. This data will enable per-protocol and CACE analyses.

Analysis of qualitative outcomes

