Adherence and protocol deviations

The definition of adherence in the intervention group is viewing of the film and receiving the structured PainSMART-questions at the initial physiotherapy consultation. Adherence to viewing of the film will be assessed through the obligatory patient reported experience measure (PREMs) questions directly after the film and patient-reported number of times viewing the film. Receiving the structured PainSMART-questions will be assessed by physiotherapists' self-reported adherence to the study protocol. The definition of adherence in the control group is receiving one question from the physiotherapist concerning the

questionnaires that the patient had filled in prior to the initial consultation. This will be assessed by physiotherapists' self-reported adherence to the study protocol.

Adherence in the intervention group will be presented as descriptive statistics (number and percentage) related to the patients' self-reporting of the number of viewings of the film (out of a maximum of two) as well as physiotherapist reported adherence to the structured PainSMART-questions at the initial physiotherapy consultation. Adherence in the control group will be presented with descriptive statistics regarding the number and percentage of patients who have received the question regarding the questionnaires at first consultation. Patients that deviate from protocol are those that, despite randomisation to the intervention group, have not answered the PREMs questions following initial exposure to the film and/or those who have reported not viewing the film at either data collection time points 1 or 2. Patients deviating from protocol are also those patients in the intervention and control groups who have not received the structured questions according to protocol, as reported by the treating physiotherapist. The number of patients deviating from the protocol will be summarised in each allocation group with details of type of deviation provided.

Minor deviation

- No exposure to the structured PainSMART-questions (intervention group)
 - * or question regarding the questionnaires at first consultation (control group)[#]
 - * In case of exposure to the film and actively cancelled physiotherapy consultation
 - # In case of exposure to baseline questionnaires and actively cancelled physiotherapy consultation

Major deviation

- No exposure to the film and the PainSMART-questions (Intervention group)

Statistical analysis population

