Physiotherapists' self-reported adherence to the study protocol will be measured using one question asking whether they adhered to the protocol by posing the structured PainSMART-questions to participating patients they met from the intervention group. Similarly, one question asking whether the physiotherapist adhered to the protocol by posing the structured question to patients in the control group will also be collected to evaluate adherence. The questions regarding adherence are answered anonymously. In the second, qualitative phase of the trial, self-reported adherence will be validated against data on adherence collected through audio recorded initial physiotherapy consultations. An independent statistician will analyse the concordance between the self-rated adherence and the objective data on adherence from consultations.

- Time Frame: collected eight months post-trial start and after all participating patients in the first part of the PainSMART-trial have had their initial physiotherapy consultation. Data on physiotherapists' adherence to protocol in the qualitative phase of the trial will be collected after all participating patients have had their initial physiotherapy consultation.
- Calculation to derive outcome:

- Adherence to study protocol will be presented descriptively in the CONSORT flow chart.

Statistical Principles

Confidence intervals and P values

For one-sided tests, the nominal level of type 1 error (α) will be 0,05 and the confidence level for two-sided confidence intervals (CI) will be 95%. The outcomes collected in the study are considered as separate entities and, therefore, restrictive multiplicity penalization of the model is not required (Dmitrienko & D'Agostino 2013). Adjustment will be made for analyses with repeated measures over time for separate test conditions using Bonferroni correction. In the case that distributional assumptions do not hold, e.g., normality etc, data transformation or non-parametric statistical alternatives will be explored.

Timing and Objectives of Interim and Final Analyses

Interim monitoring and analyses

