Patients receive seven questions and physiotherapists 3 questions regarding their experience of the initial physiotherapy consultation. Between group mean difference for responses to these questions will be analysed using independent sample t-tests. These analyses will be presented as mean and SD for each group and the between group difference in mean and CI. Three of the patient questions will be analysed for concordance with the matched physiotherapists' questions. Concordance within the intervention group and control group will primarily be analyzed by calculating intraclass correlation coefficient (ICC) with 95% confidence interval on each question as well as all three questions combined. Two-way random effects model will be used for ICC, assuming raters to be randomly selected. The ratings are single measures analyzed for consistency, to measure systematic differences between ratings. Patients and physiotherapists are treated as two independent raters, rating each of the three questions.

Sensitivity analyses

The following are all re-analyses of the primary and secondary outcomes under different conditions:

- Per-protocol analysis
- Complier average causal effect (CACE) analysis
- Responder analysis
- Complete case analysis (in case of >5% missing data)

Per-protocol analysis

Per-protocol analyses for the primary and secondary outcomes will be conducted to assess robustness of the ITT analyses and to further inform decisions regarding superiority. The sample of the patients for the per-protocol analyses will be as follows:

- Intervention group: patients receiving the PainSMART-strategy with no or minor deviation from protocol.
- Control group: patients receiving intervention with no or minor deviation from protocol.

Data on the physiotherapists' self-reported adherence to the protocol will be cross-referenced with the intervention respective control group patient consultations that each physiotherapist has conducted. This, in combination with the intervention group patients' self-reported exposure to the film, will provide data on deviation from protocol.

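### Receipt of the structured questions is counted per patient but recorded once per physiotherapist and arm, so mixed practice misclassifies patients in the exposure count and possibly in the CACE complier class

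*SAP*

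**What the plan says.** **Definition and use: the patient.** The SAP section on adherence and deviations sets the unit: "The definition of adherence in the intervention group is viewing of the film and receiving the structured PainSMART-questions at the initial physiotherapy consultation". Protocol deviators include patients in either arm "who have not received the structured questions according to protocol, as reported by the treating physiotherapist", and control adherence is reported as the "number and percentage of patients who have received the question regarding the questionnaires at first consultation". The CONSORT list in SAP, Recruitment, has a line for patients exposed to the whole strategy. Protocol, Analysis of physiotherapist adherence, says that the physiotherapists' answers, combined with patient-reported film exposure, "will provide data indicating how many of the participating patients received the full" strategy, and that this makes the per-protocol and CACE analyses possible. The CACE section of the SAP uses a two-category latent adherence class.

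**Source: the physiotherapist.** SAP, Other measures, describes "one question asking whether they adhered to the protocol by posing the structured PainSMART-questions to participating patients they met from the intervention group" and one corresponding question for control patients. Protocol, Physiotherapist data collection, describes the same instrument: "These four questions ask the physiotherapists to self-report their adherence to the study protocol for each group", together with ratings of how prepared patients were. It is collected once for the first 450 patients, about eight months after the trial began.

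**Transfer.** SAP, Per-protocol analysis: the answers are "cross-referenced with the intervention respective control group patient consultations that each physiotherapist has conducted".

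**The concern.** The unit of measurement is coarser than the unit of analysis. One answer per physiotherapist and arm does not separate that physiotherapist's patients from one another, yet the plan turns it into a patient status. Neither document gives a per-consultation adherence item for the first 450 patients, or a rule for a physiotherapist whose practice varied.

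Two results depend on this status: the count of patients exposed to the whole strategy and, if the complier class includes stage two, the CACE estimate. A wrong complier proportion rescales the complier effect, and misplaced individuals blur the complier and non-complier outcome distributions that the latent-class model has to separate.

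**Working it through.** The documents state no adherence rate, so there is no figure to reproduce. The check has a logical part and an illustrative part.

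**1. One shared value under mixed practice.** Let a physiotherapist see n patients in an arm and ask k of them. A shared yes misclassifies n − k patients and a shared no misclassifies k. The number wrong is therefore at least min(k, n − k), which is zero only when k = 0 or k = n.
- n = 4, k = 3: yes gives 1 wrong, no gives 3 wrong.
- n = 2, k = 1: exactly 1 wrong, whichever answer is given.
- n = 1: never wrong, if the answer is accurate.

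**2. The total can still be right.** Take two physiotherapists, each with n = 2 and k = 1, one answering yes and the other no. The count is 2 and the truth is 2, but two of the four patients carry the wrong status.

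**3. Workload.** Protocol, Study setting, gives about 130 physiotherapists. Half of the first 450 patients is 225, so 225/130 = 1.7 film patients each. If patients fall at random, the share of film patients whose physiotherapist has no other film patient is (129/130)^224 = 0.18. If only 60 physiotherapists took part, it is (59/60)^224 = 0.02.

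**4. Illustrative simulation.** Only 450 and 130 come from the documents. Assumed: 225 film patients allocated at random to physiotherapists; each physiotherapist's asking probability drawn from a Beta distribution with the stated mean and within-physiotherapist correlation; one yes/no answer copied to all that physiotherapist's film patients. Yes is read in three ways. Each cell shows the percentage flagged as asked / the percentage of film patients misclassified.

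| Physiotherapists | Truly asked | Correlation | Yes = any asked | Yes = at least half | Yes = all asked |
|---|---|---|---|---|---|
| 130 | 60% | 0.2 | 81.5 / 21.3 | 69.3 / 16.9 | 36.3 / 23.8 |
| 130 | 60% | 0.5 | 73.8 / 13.8 | 65.3 / 10.5 | 45.2 / 14.6 |
| 130 | 80% | 0.2 | 93.1 / 13.0 | 88.3 / 11.1 | 62.3 / 17.6 |
| 130 | 80% | 0.5 | 88.9 / 8.9 | 84.1 / 6.9 | 69.6 / 10.3 |
| 60 | 60% | 0.2 | 91.3 / 31.2 | 68.9 / 22.3 | 22.6 / 37.4 |
| 60 | 60% | 0.5 | 81.6 / 21.2 | 64.2 / 13.6 | 36.8 / 23.3 |
| 60 | 80% | 0.2 | 97.6 / 17.6 | 89.4 / 14.5 | 49.8 / 30.2 |
| 60 | 80% | 0.5 | 93.0 / 12.9 | 83.7 / 9.1 | 62.9 / 16.9 |

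In these settings 19 to 45% of film patients (130 physiotherapists) or 30 to 69% (60) sit with a physiotherapist of mixed practice. Extending the grid to 90 physiotherapists and to 75% and 90% truly asked gives overall misclassification of about 4 to 22% (at least half), 5 to 31% (any) and 6 to 37% (all).

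**5. Direction for CACE.** With a simple ITT-effect/complier-proportion ratio, the estimate is multiplied by true rate/flagged rate. At a true rate of 75%:
- Yes = at least half, flagged 80 to 85%: 0.75/0.80 = 0.94 and 0.75/0.85 = 0.88, so 6 to 12% too small.
- Yes = all, flagged 41 to 63%: 0.75/0.63 = 1.19 and 0.75/0.41 = 1.83, so 19 to 83% too large.

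The sign depends on how physiotherapists read the question, and the plan does not fix that reading.

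**The case against.** The other side has several good points.

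- **Not every patient is affected.** Actively cancelled consultations are known individually, film exposure is reported by the patient, and the final 30 to 40 consultations are audio-recorded. Physiotherapists with one patient in the arm or with uniform practice produce no error. A reader might infer that all stage-two data are worthless or that the count must be wrong; steps 1 to 3 show neither follows.
- **The response format is not given.** Protocol, Adherence promotion and monitoring, speaks of rating adherence, so the answer may be graded. It would still be one value per physiotherapist and arm, with no rule for converting it to patients, but the any/half/all readings and the percentages built on them would no longer apply.
- **The complier class is not spelled out.** The CACE section does not say that stage two is required. That follows only from the adherence definition and the protocol's statement of purpose. Since missing the structured questions is listed as a minor deviation, the class could instead follow the split between minor and major deviation.
- **The CACE ratios are only a guide.** The SAP plans a maximum-likelihood latent-class model with the baseline score as covariate. The ratio also assumes no effect in film viewers who were not asked, although they received stage one.
- **Per-protocol.** Because minor deviations stay in the set, a wrong stage-two value does not change membership for film viewers. A reader might infer that the per-protocol analysis is undermined; the SAP's own definition prevents that, apart from possible doubt over film non-viewers.

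The SAP also says the adherence answers are anonymous, which raises a separate question of whether they can be linked at all. The argument here assumes perfect linkage and still holds. The unit mismatch itself stands against all of these objections.

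**Conclusion.** The mismatch is in the text. Following the plan as written misclassifies at least one patient for every physiotherapist whose practice was mixed within an arm. The whole-strategy count can therefore be wrong, and so can the CACE complier class if it uses the SAP's adherence definition.

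The size is unknown. Under the stated assumptions, including a yes/no answer, about 4 to 22% of film patients are misclassified if yes means at least half were asked, and 6 to 37% if it means all. A reader might take the largest CACE figure, 83% too large, as the expected bias. The documents do not support that: it needs 60 physiotherapists, the strictest reading of yes and a simple ratio estimator that the SAP does not use.

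The primary ITT analysis is unaffected. This concerns a descriptive count and one sensitivity analysis, and it merits a change because the change is cheap.

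**What to change.** 1. **SAP, CACE analysis.** State what makes a patient a complier, and define the main class by patient-reported film viewing. Say how the key-message questions answered after the film and the reported number of viewings combine.
2. **SAP, Adherence and protocol deviations, and the CONSORT list.** Report stage two at physiotherapist level: the number answering that they adhered and, if answers can be linked, the number of film and control patients they treated. Do not label these as patients who received the questions.
3. **Full-strategy CACE.** Keep it only as a sensitivity analysis over a stated, wide range of true asking rates. The recorded consultations (15 to 20 film patients, physiotherapists who gave extra consent) can be shown as supporting information. They are too few and too selected to calibrate that range.

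Asking physiotherapists how many consultations included the questions would improve the overall rate but would not identify the patients, so it does not replace step 1.

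The cost is SAP wording and one extra sensitivity run; no new data are needed. The real downside is a change of estimand: the main CACE would describe film viewers, with whatever discussion followed, and not patients who received both stages.

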The study specific minimal clinical important differences (MCID) for primary outcomes at primary time points will be calculated for interpretation of the within and between-group differences. The MCIDs will be calculated for the whole cohort using an anchor method (Revicki et al, 2008). A dichotomised anchor response on the GRoC (-5- 0 = not improved; 1-5 = improved) must at least have a small association with change in the primary outcome baseline to primary time points one and two. This will be applied in a receiver operator characteristic (ROC) curve analysing the area under the curve (AUC), specificity, sensitivity and Youden index to attain an optimal cut off point for the MCIDs. MCIDs will be presented in mean and SD.

[Secondary outcome analysis](#)

[Patient reported outcome analyses](#)

-Continuous variables

Hypothesis testing for secondary outcomes for *pain intensity*, *pain self-efficacy*, *MSKP illness perceptions (BIPQ)*, *reassurance of the benign nature of MSKP*, *traditional pain coping strategies (BPCI-2, sub-scale for pain coping strategies)*, *psychological flexibility (BPCI-2 sub-scale for psychological flexibility)*, and *physical activity levels (moderate to intensive exercise, Other physical activity beside exercise, Sitting time)* will be based on analysis of group mean change from baseline. Baseline group mean scores and group mean change for each secondary outcome score from baseline to all time points for the intervention and control groups and the between-group mean change at all time points will be presented as means and CI. The within and between-group change on outcomes from baseline to 24-72 hours prior to the initial physiotherapy consultation, 24 hours post initial physiotherapy consultation and three months post-baseline will be analysed according to the ITT principle using a maximum likelihood approach for mixed models adjusted for a relevant covariance structure. The models will be adjusted for baseline covariates where relevant. Baseline factors that will be analysed for potential covariate adjustment include: age, sex, educational level, employment, pain duration, number of pain sites, comorbidities, days to initial physiotherapy consultation, previous health care interventions, ÖMPSQ risk category, self-reported sick leave and analgesic medication consumption.

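### For outcomes compared once, the SAP's one-sided 5% test and two-sided 95% interval do not match, so a result can be significant while its interval includes zero

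*SAP*

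**What the plan says.** SAP, Statistical Principles, Confidence intervals and P values, sets both levels in one sentence. Its first half covers the tests: "For one-sided tests, the nominal level of type 1 error (α) will be 0,05". Its second half turns to estimation and says that "the confidence level for two-sided confidence intervals (CI) will be 95" per cent. No level is given for a two-sided final test. The Protocol's Sample size section also uses one-sided 5%, with 80% power.

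On multiplicity, the same SAP section says that across outcomes "restrictive multiplicity penalization of the model is not required". Over time, "Adjustment will be made for analyses with repeated measures over time for separate test conditions using Bonferroni correction". It gives neither the number of comparisons k nor whether the intervals are adjusted too.

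Intervals accompany tests in several places:

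- Continuous secondary PROMs: "between-group mean change at all time points will be presented as means and CI".
- Experience items (seven from patients, three from physiotherapists): "Between group mean difference for responses to these questions will be analysed using independent sample t-tests", with the mean difference and its CI.
- Direct costs per patient: a t-test, with the mean difference and its CI.
- Preparedness as rated by physiotherapists (Secondary exploratory analysis, Intervention fidelity): a t-test, with the mean difference and its CI.

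The last three groups have one between-group comparison per outcome, so the Bonferroni rule for repeated measures does not reach them.

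**The concern.** A one-sided test at level α corresponds to a two-sided interval at 1 − 2α. One-sided 5% therefore goes with a 90% interval, and a 95% interval goes with one-sided 2.5%. Where the SAP's two levels apply to the same single comparison, following the plan exactly can give a significant p-value beside an interval that covers zero. No rule says how to report such a result. The choice of which to stress would then be made after the data are seen, and two readers of the same table could report opposite findings.

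**Working it through.** **Which level was used in the design.** The Protocol's inputs are a difference of 2 on the NRS with SD 4 (standardised difference 0.5), one-sided 5% and 80% power. The normal formula gives n per arm = 2(1.645 + 0.842)² / 0.5² = 49.5, so 50; the t-based value is 51 per arm, or 102 in total. Two-sided 5% would give 64 per arm, or 128 in total. The Protocol's figure of 102 thus matches the one-sided calculation, but as a two-arm total, whereas the Protocol calls it per group. That labelling is a separate matter and does not affect what follows. The planned total of 408 gives 204 per arm.

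**Critical values.** The 95% interval excludes zero in the favourable direction at z > 1.960. The one-sided test rejects at z(1 − 0.05/k). The matching two-sided interval level is 1 − 0.10/k. As k is not stated, a range is shown. The last column takes a true effect of 1.645 + 0.842 = 2.486 standard errors, which has 80% power at one-sided 5%. Intervals are held at 95% throughout.

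| k | One-sided level | Critical z | Matching CI | Disagreement | Chance, no effect | Chance, 80%-power effect |
|---|---|---|---|---|---|---|
| 1 | 0.0500 | 1.645 | 90% | significant, CI includes 0 | 2.5% | 9.9% |
| 2 | 0.0250 | 1.960 | 95% | none | 0 | 0 |
| 3 | 0.0167 | 2.128 | 96.7% | not significant, CI excludes 0 | 0.8% | 6.1% |
| 4 | 0.0125 | 2.241 | 97.5% | as k = 3 | 1.25% | 10.4% |
| 6 | 0.0083 | 2.394 | 98.3% | as k = 3 | 1.7% | 16.4% |

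**Largest chance of disagreement.** Let δ be the true effect in standard errors.

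- k = 1: Φ(1.960 − δ) − Φ(1.645 − δ). At δ = 0 this is 0.975 − 0.950 = 0.025. At δ = 1.8 it is Φ(0.160) − Φ(−0.155) = 0.564 − 0.438 = 0.125.
- k = 3, intervals unadjusted: Φ(2.128 − δ) − Φ(1.960 − δ). At δ = 2.05 it is Φ(0.078) − Φ(−0.090) = 0.531 − 0.464 = 0.067.

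**Illustration.** The documents give no SD for costs or experience items, so the NRS figures serve only as a scale. With SD 4 and 204 per arm, SE = 4√(2/204) = 0.396.

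- k = 1: a difference of 0.70 gives z = 1.77, one-sided p = 0.039 and 95% CI −0.08 to 1.48.
- k = 3: a difference of 0.81 gives z = 2.05, one-sided p = 0.0204 (above 0.0167) and 95% CI 0.03 to 1.59.

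**Over all outcomes compared once.** There are 1 + 10 + 1 = 12. The expected number of contradictions is 12 × 0.025 = 0.3 under no effect, and 12 × 0.125 = 1.5 if every effect lay near 1.8 standard errors. If the outcomes were independent, the chance of at least one would be 1 − 0.975¹² = 26% and 1 − 0.875¹² = 80% respectively.

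**Power if single tests move to one-sided 2.5%** (noncentral t, 204 per arm, uncorrected). At a standardised difference of 0.25, power falls from 80.9% to 71.2%. At 0.5 it goes from 99.97% to 99.90%.

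**The case against.** A reader might infer that every test in the trial is one-sided, that every interval is an unadjusted 95% one, and that the contradiction therefore runs through the whole plan, primary outcomes included. The documents do not support that.

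- The SAP's wording on one-sided tests is conditional, and no individual analysis is labelled one-sided. The null hypothesis is non-directional, the interim level has no side, and the responder comparison is a chi-square test. Against this, one-sided 5% is the only final test level stated, the sample size uses it, and the research hypotheses are directional. If some tests are two-sided, the SAP still has to say which.
- The Bonferroni sentence speaks of analyses, which does not exclude adjusted intervals. The reversal at k = 3 is therefore an assumption about both k and the intervals. For average pain and PSEQ-10, moreover, the SAP's secondary between-group comparison is the pre-consultation time point only.
- The SAP analyses the primary outcomes at two time points. With k = 2, one-sided 0.05/2 = 0.025 corresponds exactly to a 95% interval in the favourable direction. What remains is that k is unstated and that the Protocol's Analysis of primary outcomes lists three follow-ups.

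It can also be said that inference rests on the hypothesis tests and that a 95% interval is simply a measure of precision. No passage makes exclusion of zero a success criterion, so this is a fair reading. It does not prevent the contradictory pair from appearing in the results table.

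Nor do the documents show that a contradiction among the outcomes compared once is likely. The 80% figure needs nearly all effects to sit near 1.8 standard errors and the outcomes to be independent; the experience items are probably correlated.

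**Conclusion.** The mismatch is real for outcomes compared once: direct costs, the ten experience items and the exploratory preparedness rating, provided they are tested at the one stated level. The chance of a contradictory pair is 2.5% per outcome under no effect and at most 12.5%. The primary outcomes are consistent if k = 2, which the SAP should state. For secondary PROMs the reverse conflict, up to 6.7%, arises only if k = 3 and the intervals stay at 95%. The figures assume approximately normal test statistics.

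This goes beyond missing detail, because following the plan as written can produce the contradiction. It affects mainly secondary and exploratory results, and it changes no estimate or model.

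**What to change.** Amend SAP Statistical Principles before the comparative analysis:

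1. State which tests are one-sided.
2. For outcomes compared once, test at one-sided 2.5% (two-sided 5%), so that the 95% interval is the test. If one-sided 5% is kept, report 90% intervals instead.
3. For Bonferroni-corrected outcomes, state k and report intervals at the level matching the test. If tests stay one-sided at 0.05/k, this is 1 − 0.10/k: 95% for k = 2, 96.7% for k = 3. Use 1 − 0.05/k only if the tests become two-sided at 0.05/k. Pairing 1 − 0.05/k with one-sided tests would create a mismatch at k = 2, where none now exists.
4. Leave the primary comparisons at one-sided 2.5% per time point with 95% intervals (k = 2), and align the Protocol's list of time points with this.

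The cost is wording, plus some power for outcomes compared once if the stricter test is chosen: 81% to 71% at a standardised difference of 0.25 with 204 per arm, and above 99% at 0.5. Those figures are for patient-level comparisons; the preparedness rating is made by physiotherapists, so its power differs. Reporting 90% intervals costs no power, and the primary comparisons lose none under item 4.
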